6.2 Prior and Concomitant Medications

All medications which the subject has taken within 30 days prior to screening and during the study will be recorded on the CRF. The name of the drug, dose, route of administration, duration of treatment, and indication will be recorded for each medication. For combination products (e.g., Contac®), the brand name is required. For non-combination products, the generic name is desired. The use of routine ophthalmic diagnostic pharmaceutical agents (e.g., fluorescein and local anesthetic) will be allowed, and individual documentation not required. Any change in dosing parameters should also be recorded on the CRF.

All prior and concomitant medications will be coded to preferred drug names and therapeutic drug class using the *WHO Drug Dictionary*, version Enhanced B2, March 2017. Use of concomitant medications will be summarized for each therapeutic drug class and each preferred drug name by treatment group. Subjects will be counted only once under each therapeutic drug class and preferred term for which they have used at least one concomitant medication. All prior and concomitant medication data will also be listed.

The class of prior hypotensive therapy, summarized on the baseline characteristic table and listed on the washout medication listing, will also be derived from the coded medication data. Classes include the following: Prostaglandins, β -adrenoceptor antagonists, adrenergic agonists (including α -agonists such as brimonidine and apraclonidine), Muscarinic agonists (e.g., pilocarpine), Rho Kinase inhibitors, and Carbonic anhydrase inhibitors (topical or oral). For the summary table, categories will be: combination therapy, prostaglandins (monotherapy), other (monotherapy),

and no prior therapy. Additionally, the following two classes will be summarized: prior prostaglandin therapy and no prior prostaglandin therapy.

6.3 Medical and Ocular History

A medical and ocular history will be collected at screening, including diagnosis, start date, and stop date (as applicable) or ongoing. For ocular history, the applicable eye(s) will be noted. Any change in the individual's baseline health status that occur after screening and prior to first dose of study medication should be reported as medical history events.

Ocular surgery and laser procedures will also be collected at screening including the procedure description, procedure date, and affected eye(s).

All medical history and ocular surgery/laser procedures data will be presented in a by-subject listing. Medical and ocular history will be coded to preferred terms and system organ class using the Medical Dictionary for Regulatory Activities (MedDRA), version 20.0. Medical and ocular histories will be summarized for each system organ class and each preferred term by treatment group. Subjects will be counted only once under each system organ class and preferred term for which they have at least one medical/ocular history.

Study eye diagnosis will be derived from the coded ocular history data. The preferred terms of "Ocular hypertension" and "Open angle glaucoma" will be matched to the study eye selection page of the CRF. Analyses based on study diagnosis will use this definition.

7. MEASUREMENTS OF TREATMENT COMPLIANCE

All subjects will be instructed to follow once a day dosing regimen in the evening between 20:00 – 22:00 hours (8pm - 10pm). All treatments will be dosed in both eyes (OU). No formal measure of treatment compliance is planned.

8. EFFICACY EVALUATION

8.1 Overview of Efficacy Analysis Issues

8.1.1 Handling of Dropouts or Missing Data

Any missing, unused, or spurious data will be noted in the final clinical study report. Due to the small sample size caused by early study closure, not all the analyses described in the protocol for the efficacy section will be performed. The selected analyses using the observed data will be performed for informational purposes only. No imputation techniques will be used.

8.1.2 Assessment Time Windows

In general, it is intended that all safety and efficacy data (with some exceptions) will be summarized at each time point collected regardless of assessment time windows. Because subjects may have an early termination visit at any time or may have unscheduled visits, the following conventions will be implemented.

For all safety data, the visit date or start date (e.g., adverse events) will be used to calculate study day, defined as the number of days from the day of first dose. The day of first dose (Visit 3) is considered study day 1, so study day will be computed as (date of data – Visit 3 + 1). Study day will be presented in listings for medical history, concomitant medications, and adverse events.

In all by-visit safety assessments, end of study visits and early termination visits will be combined in order to present all data available for each subject; early termination visits will not be windowed into the nearest fitting study visit. Each subject will have one end of study visit.

For efficacy outcomes, early termination data will not be combined with end of study visit information as the timing of the outcome measure is integral to the analysis. Instead, the efficacy outcome will be windowed into the nearest study visit, where Week 1 visit has a ± 2 day window and Week 2 and Week 4 visits have a ± 3 day window.

8.2 Efficacy Variables and Primary Hypotheses

1. The primary efficacy outcome will be the comparison of each netarsudil group to placebo for:
 - Mean diurnal IOP within a treatment group at the Week 4 study visit (Day 29) by Goldmann Applanation Tonometry.
2. Secondary efficacy endpoints will include the comparison of each netarsudil group to placebo for:
 - Mean diurnal IOP at Weeks 1 and 2 (Days 8 and 15, respectively)
 - Mean change from baseline in mean diurnal IOP at each post-treatment visit
 - Mean percent change from baseline in mean diurnal IOP at each post-treatment visit
 - Mean IOP at each post-treatment time point
 - Mean change from diurnally adjusted baseline IOP at each post-treatment time point

- Mean percent change from diurnally adjusted baseline IOP at each post-treatment time point
 - Percentages of subjects achieving pre-specified mean, mean change, and percent mean change diurnal IOP levels at each post-treatment time point:
 - Diurnal mean IOP of ≤ 22 , ≤ 21 , ≤ 20 , ≤ 19 , ≤ 18 , ≤ 17 , ≤ 16 , ≤ 15 , ≤ 14
 - IOP reduction from baseline of ≥ 4 , ≥ 6 , ≥ 8 , ≥ 10 , ≥ 12 (IOP reduction at a visit from baseline was calculated as $\text{IOP} [\text{baseline}] - \text{IOP} [\text{visit}]$, using mean [integral or non-integral] IOP values)
 - IOP percent reduction from baseline of ≥ 5 , ≥ 10 , ≥ 15 , ≥ 20 , ≥ 25 , ≥ 30 , ≥ 35 , ≥ 40 (IOP percent reduction at a visit from baseline was calculated as $[\text{IOP reduction from baseline} / \text{IOP (baseline)}] * 100\%$)
3. The primary hypotheses are:
- H_{01} : The difference between study eyes treated with netarsudil 0.02% and study eyes treated with placebo (netarsudil 0.02% - placebo), in mean diurnal IOP at Week 4 is equal to 0.
 - H_{11} : The difference between study eyes treated with netarsudil 0.02% and study eyes treated with placebo (netarsudil 0.02% - placebo), in mean diurnal IOP at Week 4 is not equal to 0.
 - H_{02} : The difference between study eyes treated with netarsudil 0.04% and study eyes treated with placebo (netarsudil 0.04% - placebo), in mean diurnal IOP at Week 4 is equal to 0.
 - H_{12} : The difference between study eyes treated with netarsudil 0.04% and study eyes treated with placebo (netarsudil 0.04% - placebo), in mean diurnal IOP at Week 4 is not equal to 0.

Due to the early study closure, the sample size is expected to be approximately 10 ITT subjects per arm. The study will not be able to achieve the adequate power for primary hypotheses as planned. Therefore, the analyses will be performed based upon the observed data for informational purposes only. No statistical inference will be made. No subgroup analyses will be performed.

There will be no adjustment for the multiplicity of the 2 active concentrations (0.02% and 0.04%) tested against placebo in this Phase 2 study.

8.3 Analysis Methods

All continuous study assessments will be summarized by treatment and time point (as applicable) using descriptive statistics (n, mean, median, SD, minimum, and maximum). All categorical study assessments will be summarized by treatment and time point (as applicable) using frequency counts and percentages. All statistical tests will be performed at a 2-sided 5%

significance level. For the IOP measurements, 2-sided tests and 2-sided 95% confidence intervals will be reported.

Mean diurnal IOP values will be constructed by averaging the three IOP measurements on each of Week 1, Week 2, and Week 4. Mean diurnal baseline IOP will be constructed as the average of the three Day 1 IOP measurements. Mean change from mean baseline diurnal IOP will be created by taking the average of the three-time points on each of Week 1, Week 2, and Week 4 and subtracting the mean baseline diurnal IOP measurement.

For diurnally adjusted IOP measures, baseline will refer to the time-relevant measure at Visits 3.0 through 3.2 (e.g., IOP at 08:00 hours at Visit 3.0 will be the baseline for 08:00 hours at Visits 4.0, 5.0, and 6.0; IOP at 10:00 hours at Visit 3.1 will be the baseline for 10:00 hours at Visits 4.1, 5.1, and 6.1). For mean diurnal IOP, baseline will refer to the mean diurnal IOP at Visit 3. For all other variables, baseline is defined as the last measurement prior to the first dose of study medication. Change from baseline will be calculated as follow-up visit – baseline visit.

Percent change from diurnally adjusted baseline IOP will be determined by dividing the change from diurnally adjusted baseline by the corresponding baseline IOP value, such that a negative change from baseline will produce a negative percent change from baseline.

An abbreviated list of primary and secondary efficacy variables, along with the planned analysis methods for those variables, are given in Table 8-1. Note that each subject will have one eye designated as the study eye. Only study eyes will be evaluated for all the efficacy measures; however, both eyes will be treated. Fellow eyes will be evaluated separately for the primary analysis of the primary efficacy measure.

Table 8-1 Summary of Efficacy Variables and Analysis Methods

	Two Sample T-test ^a	ANCOVA ^b	MMRM ^c	Fisher's Exact Test ^d	Analysis Population	Data Used for Analysis
Primary Analysis						
Mean diurnal IOP at Week 4		X			ITT	Observed data
Secondary Analyses						
Mean diurnal IOP at Week 1 and Week 2	X	X			ITT	Observed data
Mean change from baseline in mean diurnal IOP at each post-treatment visit	X				ITT, PP	Observed data
Mean percent change from baseline in mean diurnal IOP at each post-treatment visit	X				ITT	Observed data
Mean IOP at each post-treatment time point	X	X			ITT, PP	Observed data
Mean IOP at each post-treatment time visit			X		ITT	Observed data
Mean change from diurnally adjusted baseline IOP at each post-treatment time point	X				ITT, PP	Observed data
Mean percent change from diurnally adjusted baseline IOP at each post-treatment time point	X				ITT	Observed data
Percentages of subjects achieving pre-specified mean, mean change, and percent mean change diurnal IOP levels				X	ITT	Observed data
^a Two Sample T-test comparing actual mean IOP value at each time point between each netarsudil group and placebo. ^b ANCOVA model including treatment as the main effect and baseline as the covariate. Individual models will be fit for each visit and time point. ^c Mixed Model Repeated Measures analysis including treatment as the main effect, and baseline IOP, visit, time point, treatment*visit, treatment*time point, visit*time point, and treatment*visit*time point as model terms. Repeated measures will be used to account for the correlation among measures within a subject. The model will include all post-dose visits and time points. ^d Fisher's exact test comparing the incidence in each category at each time point between each netarsudil group and placebo.						

8.3.1 Primary Efficacy Analyses

Only observed data will be used for efficacy analyses. The primary analysis of the primary outcome will employ a linear model with mean diurnal IOP at Week 4 as the response, baseline mean diurnal IOP as a covariate, and treatment as a main effect, using the ITT population. The treatment differences (netarsudil – placebo) between each netarsudil group and placebo will be

tested. The least squares mean differences (netarsudil – placebo) will be presented separately for netarsudil 0.02% and 0.04% as well as 2-sided p-values and 95% confidence intervals (CIs). However, no statistical inference will be made.

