9.6.2 Secondary Efficacy Analyses

Secondary analyses of the primary efficacy endpoint include repeating the primary analysis strategy using: observed data only, and last observation carried forward (LOCF) where LOCF will be performed using time-relevant measures. These analyses will also be repeated on the PP population to determine robustness of results. Additional imputation techniques may be designated in the formal statistical analysis plan.

Additionally, secondary analyses of the primary endpoint will be completed using individual 2-sample t-tests and 95% t-distribution CIs for each comparison netarsudil (0.02% or 0.04%) versus placebo using the ITT population.

The primary and secondary analyses will also be completed on the secondary endpoints: mean diurnal IOP at Weeks 1 and 2, mean IOP measure at each post-treatment time point and visit (08:00, 10:00, and 16:00 at the Week 1, Week 2, and Week 4 Visits), mean change from baseline in mean diurnal IOP at each post-treatment visit, and mean change from diurnally adjusted baseline IOP at each post-treatment time point and visit. Models adjusting for baseline will only be performed on the mean IOP response variable as inference is identical between this response and the change from baseline IOP response variable in such a model.

Additionally, for the mean IOP values at each time point, mixed model repeated measures will be run with baseline as the covariate; treatment, visit, time point, treatment by visit, treatment by time point, visit by time point, and treatment by visit by time point as the fixed effect factors; and subject as the random effect, repeated measure. An unstructured covariance structure will be used to model the within subject, between visit and time point variances. This allows for different variances and co-variances within and between time points and visits. The treatment by visit, treatment by time point, visit by time point, and treatment by visit by time point interactions allow for a different rate of change in IOP in the different treatment arms among visits and time points. This model will be run including the Week 1, Week 2, and Week 4 visits.

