8.3.2 Secondary Efficacy Analyses

The secondary efficacy analyses will include additional analyses of the primary efficacy endpoint as well as other analyses of the secondary endpoints, as outlined below.

The primary efficacy analysis will be repeated on the PP population.

Secondary analyses of the primary endpoint will be completed using individual two-sample t-tests and 95% t-distribution confidence intervals for each comparison (each netarsudil group vs placebo) using the ITT and PP populations.

Similar analyses will be completed on the secondary endpoints based on the ITT and PP populations: mean change from baseline in mean diurnal IOP at each post-treatment visit, mean IOP at each post-baseline time point, and mean change from diurnally adjusted baseline IOP at each post-treatment time point. Models adjusting for baseline will only be performed on the mean IOP response variable as inference is identical between this response and the change from baseline IOP response variable in such a model based on the PP and ITT populations.

Additionally, for the mean IOP values at each post-treatment time visit, mixed model repeated measures will be run with mean IOP baseline as the covariate; treatment, visit, time point, treatment by visit, treatment by time point, and treatment by visit by time point as the fixed effects; and subject as the repeated measure. An unstructured covariance structure will be used model covariances. This model will be run including the Week 1, Week 2, and Week 4 visits based on the ITT population only.

Graph will also be provided for mean IOP values by treatment group, visit, and time point.

Percent change from baseline in mean diurnal IOP at each post-treatment visit and percentage change from diurnally adjusted baseline IOP at each post-treatment time point will be analyzed using two-sample t-tests, between each netarsudil group and placebo, at each time point and visit, including two-sample t-tests and 95% t-distribution confidence intervals on the difference (netarsudil – placebo). The analysis will be based on ITT population only.

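### Does limiting every Week 4 IOP analysis to subjects observed at Week 4 call for an added MMRM contrast and a baseline-by-visit term?

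*SAP*

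**What the plan says.** SAP 8.3.1 makes the primary analysis a linear model of Week 4 mean diurnal IOP on treatment and baseline in the ITT population, and states "Only observed data will be used for efficacy analyses". SAP 8.1.1 adds "No imputation techniques will be used", giving early study closure as the reason. SAP 8.3.2 lists two further analyses of the same endpoint: "The primary efficacy analysis will be repeated on the PP population", and "Secondary analyses of the primary endpoint will be completed using individual two-sample t-tests" in ITT and PP. Each needs a Week 4 value.

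The protocol (9.5.2, 9.6.2) had planned multiple imputation for the primary analysis, with observed-data and LOCF versions as secondary. Of these, only LOCF carried Week 1 or Week 2 values forward. The imputation code in Protocol Appendix 7 conditions on treatment and baseline alone.

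The SAP keeps an ITT mixed model over Weeks 1, 2 and 4: "mixed model repeated measures will be run with mean IOP baseline as the covariate", with an unstructured covariance. SAP Table 8-1 lists it against "Mean IOP at each post-treatment time visit", and footnote c says "The model will include all post-dose visits and time points". The text names no Week 4 diurnal-average difference from this model and no baseline-by-visit term.

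SAP 8.2, 8.3.1 and 13 say that about 10 ITT subjects per arm are expected, that results are informational, and that no inference will be made.

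**The concern.** The primary analysis carries the ITT label, yet a treated subject who leaves at Week 2 contributes nothing to it. Protocol 6.18.2 lists lack of efficacy, judged from IOP readings and the Investigator's decision, among ten reasons for discontinuation. Week 4 missingness can therefore depend on Week 1 and Week 2 pressures that the ANCOVA ignores. With masked Investigators (Protocol 5.5), the natural case is one withdrawal rule for all arms. If netarsudil lowers IOP, placebo loses more of its high-pressure subjects and the estimated benefit shrinks. If netarsudil has no effect, there is essentially no bias.

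The planned MMRM could recover the lost information, but the SAP does not say that its Week 4 difference will be reported. Its single baseline slope could also misfit if the baseline relation weakens over visits. At stake is the size of the reported Week 4 difference, which still appears with a p-value and a confidence interval.

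**Working it through.** **Inputs from the documents (SAP 2.6 and 8.2).** SD 3.5 mmHg per time point, within-day correlation 0.60, difference 2.0 mmHg, two-sided 0.05, 49 or 60 per arm planned, about 10 per arm expected.

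**The plan's own figures.** SD of the diurnal mean = 3.5 × √((1 + 2 × 0.60)/3) = 2.997, which is the stated 3.0. With the noncentral t, 49 per arm gives 90.4% power and 60 per arm gives 95.2%. Both agree with the SAP. At 10 per arm, power is about 29%, and the 95% half-width for a two-group comparison is t(0.975, 18 df) × 3.0 × √(2/10) = 2.82 mmHg.

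**Assumed inputs, none in the documents.** The withdrawal rule, the loss rates and the between-visit correlations.

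**Bias when n is large.** Two arms, true difference −2.0, withdrawal when Week 2 IOP exceeds a cut-off, placebo loss 10/20/30% (active about 2/7/12%):

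| Correlation | ANCOVA | MMRM, one slope | MMRM, baseline-by-visit |
|---|---|---|---|
| flat 0.6 | −1.92 / −1.81 / −1.79 | −2.02 / −2.00 / −2.01 | −2.02 / −2.00 / −2.01 |
| baseline correlation falling 0.70, 0.55, 0.35 | −1.80 / −1.69 / −1.60 | −2.06 / −2.12 / −2.16 | −1.97 / −1.99 / −1.98 |

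The direction is as feared. The single-slope MMRM is sound when the baseline relation is stable. It overshoots by 0.06 to 0.16 mmHg here when that relation decays, and by 0.02 to 0.11 in a second set of runs.

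**Accuracy at 10 per arm.** Bias alone does not settle which estimate is better, so combine it with the spread: RMSE = √(bias² + SD²). From 400 two-arm trials per row, with bias measured from −2.0 and a Monte Carlo error of about 0.05 to 0.075 on each mean:

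| Correlation, placebo cut-off | ANCOVA bias, SD, RMSE | Baseline-by-visit MMRM bias, SD, RMSE |
|---|---|---|
| flat, 10% | 0.11, 1.08, 1.09 | 0.00, 1.10, 1.10 |
| flat, 20% | 0.15, 1.20, 1.21 | −0.02, 1.25, 1.25 |
| flat, 30% | 0.30, 1.23, 1.27 | 0.08, 1.29, 1.29 |
| falling, 10% | 0.17, 1.29, 1.30 | −0.01, 1.30, 1.30 |
| falling, 20% | 0.40, 1.27, 1.33 | 0.13, 1.32, 1.33 |
| falling, 30% | 0.46, 1.50, 1.57 | 0.08, 1.49, 1.49 |

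The model is slightly worse in three rows, level in two and about 5% better in the most extreme row. These runs are small.

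Larger three-arm runs are steadier. With 6,000 trials per scenario, between-visit correlation 0.7/0.6/0.5, a cut-off rule and placebo loss 29% (active 11%), the ANCOVA bias is 0.32 and the model's is 0.00, but RMSE is 1.34 for both. In variance terms, 1.34² = 1.80. The ANCOVA's share from bias is 0.32² = 0.10, leaving 1.69 (SD 1.30). The model has no bias but a variance of 1.80. The 0.10 saved in squared bias is spent on variance. In a separate set of 16 scenarios, RMSE agreed within about 1 to 1.5% (for example 1.298 against 1.303 at 23% placebo loss), and the model was closer to the truth in 48 to 53% of trials.

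**Bias against uncertainty.** 0.05/2.82 = 2% and 0.4/2.82 = 14% of the half-width. The interval does not narrow under the model.

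**Is the contrast available?** The MMRM contains treatment-by-visit and treatment-by-visit-by-time-point terms. The Week 4 difference averaged over 08:00, 10:00 and 16:00 is therefore a linear combination of terms already fitted. SAP 8.3.2 omits visit-by-time-point and Table 8-1 footnote c lists it. With the three-way term present, both versions give the same 27 cell means.

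**The case for a change.** The best case for a change is that it costs almost nothing: one model term, one LS-mean line and one Table 8-1 entry. The estimate is what a reader takes from an informational analysis, and two separate sets of simulations agree that the ANCOVA is attenuated and that baseline-by-visit slopes repair it. Naming the contrast in advance also prevents a choice after unmasking. The planned model has 9 × 10/2 = 45 covariance parameters for about 30 subjects, and no fallback structure is stated.

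The textual reading and the direction of bias stand. So does one limit on a possible reply. SAP 8.1.2 assigns early-termination IOP to the nearest visit window, but this helps only for exits within Day 29 ± 3, and the early-discontinuation visit requires only the 08:00 reading. It does not rescue a subject who leaves at Week 2.

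The rest does not carry. The larger losses modelled are generous: Protocol 4.1 enrols 60 where 49 are needed, an allowance of 11/60 = 18% for non-completion and disqualification together, whereas the runs take placebo IOP-driven loss as high as 41%. If loss depends on unobserved IOP, the repair is only partial: ANCOVA bias is 0.23 to 0.45 and MMRM bias 0.19 to 0.34 at 20 to 24% placebo loss. The ANCOVA is already fixed as primary, so there is no post hoc choice of main result. SAP 1 and 11 allow additional analyses if they are identified in the study report. Table 8-1 describes itself as abbreviated, and the table shells, which may list the contrast, were not available to check.

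**Conclusion.** No change is needed. The observed-data analyses can understate a real effect by roughly 0.05 to 0.4 mmHg if withdrawal follows IOP, with no bias to speak of if the drug does nothing. At about 10 per arm, an estimate with an SD of about 1.1 to 1.5 mmHg gains nothing material in overall accuracy from the richer model. The unnamed Week 4 contrast is a detail that an analyst can produce from the planned MMRM without altering it. The baseline-by-visit term matters only if the baseline relation decays over visits, which the documents neither state nor rule out. Dropping LOCF is no loss: in the flat-correlation runs it overshot by 0.06 to 0.35 mmHg.

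This rests on the SAP's expected sample size, its commitment to make no inference, and dropout rules and correlations that are assumed. At the originally planned 60 per arm, with a formal superiority claim, the balance of bias and variance would need to be weighed again.
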